## 5 General Analysis Issues

### 5.1 Analysis Software

Analysis will be performed using SAS® Software version 9.3 or later whenever possible. Other software packages, including R and StatXact®, may be used for particular specialized procedures.

### 5.2 Methods for Withdrawals, Missing Data, and Outliers

Per the intention-to-treat principle, subjects who withdraw from the study or are lost to follow-up will have all available data used in the analysis. In the event that a substantial number of subjects are withdrawn or lost to follow-up, baseline characteristics and available information on hospital course will be reviewed and compared to subjects not withdrawn or lost, to assess empirically if these subjects differ from those remaining in the study for the scheduled treatment and follow-up time.

Data from the follow-up surveys will be collected in such a way that data for a particular day should be complete. Information may be missing, however, if an entire day is not completed. For cases where the information needed to derive the primary outcome is incomplete, multiple imputation methods will be used. This is described in more detail in Section 7.2.

Outliers will be reviewed for validity. Outliers that are valid, for example, high number of vomiting episodes, will be included in all primary reports from this trial.

### 5.3 Multicenter Studies

The randomization sequences will be stratified by clinical center, to assure approximate balance of sites between study arms at all times. The primary analysis, and other analyses

will be stratified by clinical center in order to account for possible baseline differences between centers.

## 5.4 Multiple Comparisons

The secondary outcomes will be subject to adjustment of significance level for multiple comparisons. Diarrhea duration, vomiting duration, return visits, missed daycare, missed work, and household transmission rate will be subject to Holm's stepdown procedure. Specifically, the smallest of the six p-values will be compared to a significance level of 0.05/6. If significance is reached, the next-smallest p-value will be compared to 0.05/5, and so on. The final p-value of the six will be compared to 0.05, assuming that all others are significant. Confirmatory and tertiary outcome results will not be adjusted for multiple comparisons, as these are more exploratory in nature.

## 5.5 Planned Subgroups, Interactions, and Covariates

There are three subgroup factors prespecified for formal analysis in this trial:

1. Age (under 1 year versus 1 and older)
2. Antibiotic useage during the 14 days prior to ED visit,
3. Infectious agent: virus, bacteria, parasite, or other/unidentified.

We will also consider the factor used to randomize, duration of symptoms (<48 hours vs. 48 hours or more), in subgroup analyses.

## 5.6 Derived and Computed Variables

All derived and computed variables will be outlined in the analysis dataset specifications for this study. These datasets are independently programmed by two statisticians. The SAS COMPARE procedure will be used to verify that the dual programmed analysis datasets are identical for each variable and each observation.

## 5.7 Independent Review

All statistical analyses for primary reporting of trial results will be independently verified through dual programming. Two statisticians will each program all datasets and analyses for the DSMB reports and the primary manuscript(s) and the results will be compared. This process will begin at the analysis design stage and will continue through writing of abstracts and manuscripts.

## 6 Overview of Planned Analyses

### 6.1 Schedule of Interim Analyses

This study has two planned *formal* interim analyses. There will be additional meetings for review of the protocol, safety of the first 80 patients, and other meetings, as necessary. Formal interim analyses will examine treatment efficacy as well as patient safety. These analyses will be reviewed by the DSMB. The DSMB will, at their discretion, be able to request analyses additional to those described in this SAP.

The total target enrollment for this study is 900 subjects. We estimate that this will take 4 years. The first analysis (safety) will take place after enrollment of 80 subjects (40 of these  $<1$  year old and  $40 \geq 1$ ). The first formal efficacy interim analysis will take place after the second year of enrollment, after approximately 350 subjects have been enrolled. The second formal efficacy interim analysis will be performed after approximately 620 subjects have been enrolled. The DSMB is to review interim data and make recommendations regarding continuation or modification of the study.

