## 1.4 Subject Eligibility, Accrual and Study Duration

Eligible participants will be identified by on-site study staff. Inclusion criteria are:

1. Age 3-48 months (have not yet reached their fourth birthday); AND
2. Presence of 3 or more watery stools within 24 hours of screening; AND
3. Duration of vomiting or diarrhea less than 7 days; AND
4. Symptoms consistent with acute intestinal infectious process.

We will exclude subjects with any of the following:

1. Presence of an indwelling vascular access line; OR
2. Presence of structural heart disease excluding non-pathological heart murmurs; OR
3. Receiving immunosuppressive therapy or history of immunodeficiency; OR
4. Hematochezia in the preceding 48 hours; OR
5. Chronic gastrointestinal problems (e.g. short gut syndrome, inflammatory bowel disease); OR
6. Patients with known pancreatitis; OR
7. History of abdominal surgery; OR
8. Critically ill patients; OR
9. Family member with an indwelling vascular access line, or on immunosuppressive therapy, or with a known immunodeficiency; OR
10. Bilious emesis; OR
11. Probiotic use (supplement) in the preceding 2 weeks; OR
12. Oral or intravenous steroid use in the preceding six months; OR
13. Previously enrolled in this trial; OR
14. Allergy to lactobacillus or Microcrystalline Cellulose (MCC); OR
15. Allergy to erythromycin, clindamycin, AND  $\beta$ -lactam antibiotics (all); OR
16. Not available for daily follow-up while symptomatic; OR
17. Parent/guardian not speaking English or Spanish; OR
18. Under 6 months old AND premature (<37 weeks).

The trial is anticipated to enroll 970 subjects over four years, which will include four acute gastroenteritis seasons. An interim safety analysis will be prepared for Data Safety Monitoring Board (DSMB) review after the first 80 subjects (half of whom will be under 1 year of age) have been followed for 1 month. At the time of this review, the DSMB *may* alter the subsequent sample size based on overall event rates.

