### 5.3 Sample Size Calculations and Statistical Power

The primary analysis will be performed on a binary outcome: development of moderate-to-severe disease. The power of this analysis is based on the proportion of patients with moderate-to-severe disease. Our pilot data indicate that 25% of patients will have moderate to severe disease during the course of their illness. Furthermore expert surveys indicated that an absolute risk reduction of 10% would constitute a minimal clinically-important difference (MCID). Therefore our sample size calculation assumed a 25% event rate in the control group for which we desire to detect an absolute beneficial treatment effect of 10% with 90% power. Using a two-sided type I error ( $\alpha$ ) of 0.05 and the hypothesized proportions yields a required total sample size of 670 patients. Our expected power, should we find different event rates in our 2 groups, is displayed in [Table 2 on the next page](#).

Based on previous work by our group, we assumed a 10% loss to follow up ( $670/0.90 = 744$ ), 5% drop out, and 3% drop in (caregivers who buy a probiotic agent

Outcome Control	Outcome Intervention	% Difference	Power
0.30	0.21	9%	0.76
0.30	0.20	10%	0.85
0.25	0.15	10%	0.90
0.25	0.16	9%	0.82
0.25	0.17	8%	0.72
0.20	0.10	10%	0.95
0.20	0.12	8%	0.81
0.20	0.13	7%	0.69

Table 2: Power Analysis

to administer to their child) rate ( $744/(0.92)^2 = 879$ ). Adjustment for O’Brien-Fleming monitoring boundaries requires a further 2% increase. Thus, the total number randomized (final sample size) will be 897.

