## 5.4 Recruitment Estimates and Attrition

### 5.4.1 Recruitment

To estimate the number of subjects with acute gastroenteritis of eligible ages that would meet all inclusion criteria and be enrolled annually, we obtained discharge diagnoses from all study sites for 2005-2011. In 2011, the study sites evaluated 14,048 potentially eligible subjects (patients 3-48 months with ICD9 codes for diarrhea) out of 507,039 total emergency department visits (2.8%). In the past 7 years the lowest proportion of such patients per total emergency department volume was 2.3% (2008). Therefore, using 2011 emergency department volumes and lowest proportion of patients with diarrhea our conservative estimate for eligible patients would be 11,150 patients 3-48 months with diarrhea per year (or 30 patients per day network wide). Our best estimate is that 4.5% of children with acute gastroenteritis aged 3-48 months will be enrolled. We plan to enroll 225 patients/year and 970 subjects over 4 acute gastroenteritis seasons.

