## 8.2 Frequency of Interim Analysis:

The Data Safety Monitoring Board (DSMB) will meet after 80 patients (safety end points for 1 month), approximately 350 patients (end of 2nd year of enrollment) and 620 patients (end of 3rd year of enrollment) to review enrollment, study procedures, loss to follow-up, drop-in rate, and interim safety and efficacy results. The analyses will test the hypothesis that the probability of developing moderate-to-severe acute gastroenteritis in the probiotic arm is equal to that in the placebo arm. An analysis will also be conducted after 20 subjects under 6 months of age have been enrolled. The DSMB is to review interim data and make recommendations regarding continuation or modification of the study based on safety in this age group. Conservative O'Brien-Fleming monitoring boundaries, implemented using the Lan-DeMets  $\alpha$ -spending function approach, will be used as guidelines for early stopping for efficacy.

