### **B) Changes made in February 2017 (V2.0 to V3.0)**

1. Increased sample size from 900 to 970 following discovery that up to 36 patients were potentially exposed to lower probiotic dosing (pages 8, 11 and 26)

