### 3.3 Sample Size and Power Determination

The primary outcome is binary: whether total post-enrollment Modified Vesikari Score (MVS) is  $\geq 9$  during the 2-week follow-up period. The difference between arms will be tested at a 0.05 level. The null and alternative hypotheses are, respectively,

$$H_0 : p_A = p_P \quad \text{and} \quad H_1 : p_A \neq p_P,$$

where  $p_A$  and  $p_P$  are, respectively, the true probabilities of  $MVS \geq 9$  on the Active drug and on Placebo.

Our pilot data indicate that 25% of patients will have moderate to severe disease ( $MVS \geq 9$ ) during the course of their illness. Furthermore, expert surveys indicated that an absolute risk reduction of 10% would constitute a minimal clinically-important difference (MCID). Therefore, our sample size calculation assumed a 25% event rate in the control group for which we desire to detect an absolute beneficial treatment effect of 10% with 90% power (0.1 Type II error rate). Using a two-sided type I error ( $\alpha$ ) of 0.05 and the hypothesized proportions yields a required total sample size of 670 patients. Our expected power, should we find different event rates in our 2 groups, is displayed in the following table.

Placebo	Active	% Difference	Power
0.30	0.21	9%	0.76
0.30	0.20	10%	0.85
0.25	0.15	10%	0.90
0.25	0.16	9%	0.82
0.25	0.17	8%	0.72
0.20	0.10	10%	0.95
0.20	0.12	8%	0.81
0.20	0.13	7%	0.69

Based on previous work by our group, we assumed 10% loss to follow-up ( $670/0.90 = 744$ ), 5% drop-out, and 3% drop-in (caregivers who buy a probiotic agent to administer to their child) rate ( $744/(0.92)^2 = 879$ ). Adjustment for O’Brien-Fleming monitoring boundaries requires a further 2% increase. Thus, the total number randomized (final target sample size) will be 900.

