## Lactobacillus Rhamnosus GG vs. Placebo for Pediatric Acute Gastroenteritis

### Summary of SAP changes (from version 1.1- January 2015- to V1.2 April 2017)

1. Section 7.2: The definitions of duration of diarrhea and vomiting were changed to incorporate additional details about handling potentially erroneous dates and times. (Pages 13 and 14)
2. Section 7.2.1: Detail was added on the approach for combining results from nonparametric tests across imputed datasets. (Page 15)
3. Section 7.2: A sensitivity analysis was added. This will look at the primary results after excluding subjects with daily surveys that were completed more than 14 days after the corresponding survey day. (page 16)
4. Section 7.4: Diaper rash was added as one of the symptoms not counted in the initial “side effects” window due to an expected high prevalence at baseline and early follow-up. (Page17)
5. Section 7.6: Detail was given on the analysis of subgroup effects related to count outcomes (negative binomial regression). (page 18)

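### SAP V1.2 keeps a target of 900, and stopping levels computed for 900, although protocol V3.0 had already raised enrollment to 970

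*Combined protocol and SAP*

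**What the plan says.** **Protocol V3.0 (February 2017).** Section 1.4: "The trial is anticipated to enroll 970 subjects over four years". The abstract also gives 970. The reason appears only in the summary of protocol changes: "Increased sample size from 900 to 970 following discovery that up to 36 patients were potentially exposed to lower probiotic dosing". The sample size derivation in 5.3 was left as it stood and ends: "the total number randomized (final sample size) will be 897". Section 5.4.1 reads: "We plan to enroll 225 patients/year and 970 subjects over 4 acute gastroenteritis seasons". Section 8.2 places the efficacy looks at "approximately 350 patients (end of 2nd year of enrollment) and 620 patients (end of 3rd year of enrollment").

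**SAP V1.2 (April 2017).** Section 3.3: "the total number randomized (final target sample size) will be 900". Section 6.1: "The total target enrollment for this study is 900 subjects", with efficacy looks at about 350 and 620 subjects. Section 6.2 specifies two-sided O'Brien-Fleming boundaries by alpha spending. It gives interim levels of 0.00065 and 0.0136 if the analyses are held as planned, and a final level of 0.0457 if the planned total is reached. It states that total type I error will not exceed 0.05. The number 970 appears nowhere in this SAP.

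**Dating.** The SAP change list is headed "Summary of SAP changes (from version 1.1- January 2015- to V1.2 April 2017"). It has five items, and none concerns the sample size or the boundaries.

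**The concern.** The conflict is between the current protocol text and the current SAP text. The change lists serve only to date the versions and to supply the reason for 970. The SAP was reopened after the protocol had raised the target, yet it kept the old number in two places.

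The number matters in the SAP because the boundaries depend on it. The 0.0457 is the only final threshold printed for the primary test. It is tied to the planned total, which the SAP defines only as 900 and the current protocol defines as 970. A reader at the final analysis could apply 0.0457 at 970 or recompute it, and a recomputed level depends on what was done at the interims. At stake is which threshold governs a primary p-value close to 0.046, and whether the promise of at most 0.05 holds.

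**Working it through.** **Inputs.** Looks at 350 and 620 (SAP 6.1, protocol 8.2); totals of 900 (SAP 3.3, 6.1) and 970 (protocol 1.4, 5.4.1); printed levels 0.00065, 0.0136 and 0.0457 (SAP 6.2); overall two-sided alpha 0.05. Enrolled counts are used as information. That is an assumption; the fractions hold if losses are similar across looks.

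**Spending function.** Lan-DeMets O'Brien-Fleming type, 0.025 per side. The cumulative two-sided alpha is α(t) = 4·[1 − Φ(2.2414/√t)], where 2.2414 is the 0.9875 normal quantile. Levels after the first look come from recursive numerical integration.

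**Step 1: reproduce the printed levels at 900.** t = 350/900 = 0.3889 and 620/900 = 0.6889.
- First look: 2.2414/√0.3889 = 3.594, so α = 4 × 0.000163 = 0.00065.
- Solving the later looks gives 0.01363 and 0.04572.

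These match the printed 0.00065, 0.0136 and 0.0457. Alternatives do not match: a total of 897 gives 0.00067/0.0138/0.0457; looks at 35% and 70% give 0.0003/0.0147/0.0455; classical O'Brien-Fleming gives 0.0013/0.0155/0.0445. The printed set therefore belongs to 900.

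**Step 2: levels for 970.** t = 350/970 = 0.3608 and 620/970 = 0.6392. The levels are 0.00038, 0.00998 and 0.04683.

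**Step 3: total error if 0.0457 is kept as the final level.** Using all three printed levels:
- at 900: 0.00065 + 0.01317 + 0.03615 = 0.04997
- at 970: 0.00065 + 0.01317 + 0.03695 = 0.05077

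The total rises because the second look shares less information with the final test. Their correlation falls from √0.6889 = 0.830 to √0.6392 = 0.799.

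| Interim levels used (looks at 350 and 620 of 970) | Alpha spent at interims | Total with 0.0457 | Final level giving 0.05 |
|---|---|---|---|
| Both as printed | 0.01382 | 0.0508 | 0.0449 |
| Both set for 970 (0.00038, 0.0100) | 0.01011 | 0.0489 | 0.0468 |
| First as printed, second reset to 0.0098 | – | 0.0490 | 0.0468 |

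A simulation of 20 million trials gave 0.05077, 0.04891 and 0.04894 for the three rows.

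**Step 4: other look times.** The documents do not report when the looks were held. Looks at 35% and 70% of 970, the fractions used in the SAP 4.3 simulations, give 0.0498 with printed interim levels and 0.0502 with levels set for 970. Moving only the second look (assumed values), printed / set for 970: 570 gives 0.0515 / 0.0480; 650 gives 0.0503 / 0.0496; 670 gives 0.0500 / 0.0500.

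**Step 5: dependence on the test statistic.** Steps 1 to 4 need a standard normal combined Z. SAP 4.3 weights the two stage statistics by n1/(n1+n2) and n2/(n1+n2), without square roots. The null variance at the final analysis is then (n1² + n2²)/(n1+n2)². With n1 = 350 and n2 = 620 this is 506,900/940,900 = 0.54, not 1. Simulated with those weights and no enrichment, total error is 0.0065 at 900 and 0.0072 at 970.

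**Step 6: the protocol's own figures.** The chain 670/0.90 = 744; 744/0.92² = 879; 879 × 1.02 = 896.6 reproduces 897. Nothing in 5.3 leads from there to 970. On accrual, 4 × 225 = 900, whereas 970/4 = 242.5 per year.

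**The case against.** The strongest reply is that alpha spending is itself the recomputation rule. SAP 6.2 names the approach, and protocol 8.2 names the Lan-DeMets form. Each level follows from the information fraction and the alpha already spent. The printed levels are conditional, and SAP 4.3 allows for unplanned looks, whose levels could only come from recalculation. On this reading 0.0457 illustrates a plan that no longer applies, and nobody is bound to use it at 970. In addition, the error moves by only +0.0008 or −0.0011 with looks at 350 and 620, the sign is unknown, and the figures apply only once the weights in SAP 4.3 are corrected, which is a much larger issue.

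Most of this stands. The method can handle 970, the printed levels are correct for 900, and the effect is small. Nor does the 897 in protocol 5.3 make the power calculation wrong; only its description as the final size is out of date. What the reply does not remove is the ambiguity. The condition on 0.0457 refers to the anticipated total, which is 900 in the SAP and 970 in the protocol, so the level could be applied at 970 on the documents as written. No sentence says that it will be recomputed, and the recomputed value is 0.0449 or 0.0468 depending on facts the documents do not give.

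**Conclusion.** The point holds and is minor. The SAP's target size is out of date, and its only final significance level belongs to a total that the trial no longer plans. With looks at 350 and 620 of 970, keeping 0.0457 gives a total error of 0.0508 with printed interim levels and 0.0489 with interims set for 970. The conclusion could change only for a final p-value between 0.0449 and 0.0457 in the first case, or between 0.0457 and 0.0468 in the second. The documents show that the final level must be checked, not that it must become stricter. These sizes rest on enrolled counts as information, on assumed interim timing and levels, and on a combined Z that is standard normal, which requires the separate weighting point in SAP 4.3 to be corrected first.

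**What to change.** - **SAP 3.3 and 6.1:** state 970.
- **SAP 6.2:** replace the fixed 0.0457 with a rule. The final level is computed before the final analysis from the same Lan-DeMets O'Brien-Fleming function, using the alpha actually spent at the interims held and the actual information fractions. Record the interim dates, counts and levels used. As illustrations, the result is 0.0449 if the printed levels were applied at 350 and 620 of 970, and 0.0468 if the interims were set for 970.
- **Protocol 5.3:** add a sentence linking 897 and 900 to 970, with the reason now found only in the change summary.
- **Protocol 5.4.1:** reconcile 225 per year over four seasons (900) with 970 (242.5 per year).

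The cost is a few text corrections and one recalculation. The one downside is that the final threshold may end up slightly stricter or slightly looser than 0.0457.

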### 6.2 Stopping Rules for Interim Analyses

Two-sided O'Brien-Fleming boundaries, implemented using the alpha-spending function approach will be used. Specifically, if the analyses are performed exactly when planned, the significance levels that will be used at interim analyses are 0.00065 and 0.0136. If the trial reaches the anticipated total sample size, a significance level of 0.0457 will be used for the final test. These boundaries assure that the total Type I error rate will be less than or equal to 0.05.

### 6.3 Blinding in the Interim Analyses

Data center biostatisticians involved in this study will be partially blinded, aware of results by treatment arm, but not of arm identities. Other data center personnel will be blinded to treatment assignments, but data center study team for this trial will have access to individual safety and efficacy data. Personnel at the clinical centers will be blinded to aggregate safety and efficacy data until the time of final analysis or until the decision is made to unblind all investigators to study results.

All by-treatment interim analyses will refer to arms as "A" and "B" throughout the report presented to the DSMB. The DSMB will have the option of being unblinded to treatment arm identity at any time.

## 6.4 Schedule of Final Analyses

All final, planned analyses identified in the protocol and in this SAP will be performed only after all randomized patients have completed the protocol and the results of all significant queries have been resolved. Any *post hoc*, exploratory analyses completed to support planned study analyses, which were not identified in this SAP, will be documented and reported as such in all study publications.

# 7 Planned Analyses with Procedures for Completion

## 7.1 Analysis of Demographic and Other Pre-Treatment Characteristics

Publication of the primary results will include reporting of key baseline characteristics overall, and by assigned treatment arm. These will include, but are not limited to

- gender
- race
- age
- baseline MVS
- duration of symptoms prior to enrollment (<48 hours vs. 48 hours or more)
- breast-feeding status
- antibiotic useage during the 14 days prior to ED visit
- infective agent at baseline (e.g., norovirus, rotavirus)
- hydration assessment (Gorelick dehydration score)
- need for hospitalization from initial ED visit

